27. Subject has HBV, HCV, or human immunodeficiency virus (HIV) infection defined as:
 - HBV: hepatitis B surface antigen (HBs Ag) positive (+) or detected sensitivity on the HBV deoxyribonucleic acid (DNA) polymerase chain reaction (PCR) qualitative test for subjects who are hepatitis B core antibody (HBc Ab)

- positive (+) subjects (and for Hepatitis B surface antibody positive (+) subjects where mandated by local requirements);
- HCV: HCV ribonucleic acid (RNA) detectable in any subject with anti-HCV antibody (HCV Ab);
 - HIV: confirmed positive anti-HIV antibody (HIV Ab).
28. Prior or current gastrointestinal (GI) dysplasia, other than completely removed low-grade dysplastic lesion in any biopsy performed during or before the Screening endoscopy.
29. History of any malignancy, except for successfully treated nonmelanoma skin cancer (NMSC) or localized carcinoma in situ of the cervix.
30. History of spontaneous gastrointestinal (GI) perforation (other than appendicitis or mechanical injury), diverticulitis or significantly increased risk of GI perforation per investigator's judgment.
31. Screening laboratory and other analyses show any of the following abnormal results:
- Serum Aspartate Transaminase (AST) or Alanine Transaminase (ALT) $> 2 \times$ upper limit of normal (ULN);
 - Estimated glomerular filtration rate (eGFR) by simplified 4-variable Modification of Diet in Renal Disease (MDRD) formula $< 30 \text{ mL}/\text{min}/1.73 \text{ m}^2$;
 - Total White Blood Cell (WBC) count $< 2,500/\mu\text{L}$;
 - Absolute neutrophil count (ANC) $< 1,200/\mu\text{L}$;
 - Platelet count $< 100,000/\mu\text{L}$;
 - Absolute lymphocytes count $< 750/\mu\text{L}$;
 - Hemoglobin $< 9 \text{ g}/\text{dL}$.
32. Female subject who is pregnant, breastfeeding or considering becoming pregnant during the study and within 30 days after the last dose of study drug, or has positive pregnancy test at Screening (serum) or Baseline (urine).

33. History of an allergic reaction or significant sensitivity to constituents of the study drug (and its excipients) and/or other products in the same.
34. History of clinically significant (per investigator's judgment) drug or alcohol abuse in the last 6 months.
35. Subject who previously received stem cell transplantation
36. Subject has been a previous recipient of an organ transplant which requires continued immunosuppression.

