If any urine pregnancy test is positive, a serum pregnancy test will be performed by the central laboratory. If the serum pregnancy test is positive, dosing must be stopped and the subject must be discontinued from the study or, if pregnancy is identified at end of study visit, pregnancy must be reported to AbbVie as outlined in Section 6.1.6.

A lactating or pregnant female will not be eligible for participation or continuation in this study.

If during the course of the study a woman becomes surgically sterile or postmenopausal and complete documentation as described in Section 5.2.4 is available, pregnancy testing is no longer required.

COVID-19 Pandemic-Related Acceptable Protocol Modifications

Monthly urine pregnancy testing must be performed for women of child-bearing potential and results confirmed prior to administration of study drug to the subject. Urine pregnancy tests may be performed at the local lab or at home and confirmed by site staff via phone, telemedicine or video call. Pregnancy test results must be available before drug dispensation.

Hepatitis Screen

All subjects will be tested for the presence of HBV and HCV at Screening.

Hepatitis B

Subjects will be tested for the presence of HBV at screening using the following tests:

- HBs Ag (Hepatitis B surface antigen)
- HBc Ab/anti-HBc (Hepatitis B core antibody)
- HBs Ab/anti-HBs (Hepatitis B surface antibody)

[figure not shown]
HBV serologic test results will be interpreted and managed as shown in [Figure 4](#).

- A positive result for HBs Ag will be exclusionary.
- A negative result for HBs Ag will trigger automatic reflex testing for core antibodies (HBc Ab) and surface antibodies (HBs Ab).
- For a subject who has had an HBV vaccination (should document in the medical history), a positive test result for HBs Ab is expected, the HBV DNA

PCR qualitative testing is not required and the subject may be enrolled (Scenario B).

- A negative test result for HBc Ab does **not** require HBV DNA PCR qualitative testing and the subject may be enrolled (Scenarios A and B).
- A positive test result for HBc Ab requires HBV DNA PCR testing (automatic reflex testing) (Scenarios C and D).
- A positive result for HBV DNA or a result that exceeds detection sensitivity will be exclusionary.
- A subject with a negative result for HBV DNA may be enrolled.

Figure 4. Interpretation and Management of HBV Serologic Test Results

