* A positive test result for HBs Ab is expected for subjects who have had a HBV vaccination. For subjects without a history of HBV vaccination (and for subjects in Japan) a positive result for HBs Ab/anti-HBs requires HBV DNA PCR testing.

** Where mandated by local requirements; subjects with HBs Ab+ and/or HBc Ab+ and negative HBV DNA at Screening should have HBV DNA PCR testing performed approximately every 12 weeks. HBV DNA PCR testing every 12 weeks is not necessary when the subject has a history of HBV vaccine and HBs Ab+ and HBc Ab-. If necessary, HBV DNA PCR may be tested at unscheduled visits.

COVID-19 Pandemic-Related Acceptable Protocol Modifications

In the event that the HBV DNA PCR cannot be performed for subjects who require the test due to study modifications related to the COVID-19 pandemic, perform the HBV

DNA PCR at the next earliest feasible visit or arrange to have it completed by a local laboratory.

Hepatitis C

Blood samples for hepatitis C serology will be obtained at the Screening Visit. A positive HCV Ab will trigger an HCV RNA test. A subject will not be eligible for study participation if test results indicate active hepatitis C (HCV RNA detectable in any subject with anti HCV Ab).

HIV

Subjects with HIV infection (positive HIV test) are excluded from study participation. An anti-HIV antibody (Ab) test will be performed at Screening, unless prohibited by local regulations. The investigator must discuss any local reporting requirements to local health agencies with the subject. The site will report confirmed positive results to their health agency per local regulations, if necessary. If a subject has a confirmed positive result, the investigator must discuss with the subject the potential implications to the subject's health and subject should receive or be referred for clinical care promptly. **AbbVie will not receive results from the testing and will not be made aware of any positive result.**

Clinical Laboratory Tests

Blood samples will be obtained for the laboratory tests listed in [Table 1](#). Tests should always be performed only after all clinical assessments, questionnaires (Inflammatory Bowel Disease Questionnaire [IBDQ], etc.) and vital sign determinations are obtained during a visit.

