AST or ALT	
 • Interrupt study drug immediately if confirmed ALT or AST $> 3 \times$ ULN by repeat testing with new sample and either a total bilirubin $> 2 \times$ ULN or an international normalized ratio (INR) > 1.5. 
 ○ A separate blood sample for INR testing will be needed to measure INR at the time of repeat testing for ALT or AST. A repeat test of INR is not needed for determination if above toxicity management criteria are met. • Interrupt study drug immediately if confirmed ALT or AST $> 3 \times$ ULN by repeat testing with new sample along with appearance of fatigue, nausea, vomiting, right upper quadrant pain or tenderness, fever, rash, and/or eosinophilia ($> 5\%$). • Interrupt study drug immediately if confirmed ALT or AST $> 5 \times$ ULN by repeat testing with new sample for more than 2 weeks. • Interrupt study drug immediately if confirmed ALT or AST $> 8 \times$ ULN by repeat testing with new sample. • Subjects with HBc Ab+ (irrespective of HBs Ab status) and negative HBV DNA PCR testing at screening who develop the following should have HBV DNA by PCR testing performed within 1 week (based on initial elevated value): 
 ○ ALT $> 5 \times$ ULN OR ○ ALT or AST $> 3 \times$ ULN if an alternative cause is not readily identified. 
 • A separate blood sample for HBV DNA PCR testing will be needed at the time of repeat testing for ALT or AST. 
A positive result for HBV DNA PCR testing in these subjects will require immediate interruption of study drug (unless not acceptable by local practices) and a hepatologist consultation should occur within one week for recommendation regarding subsequent treatment.
 
Subjects who meet any of the above criteria should be evaluated for an alternative etiology of the ALT or AST elevation and managed as medically appropriate. If applicable, the alternative etiology should be documented in the eCRF. If ALT or AST values return to the normal reference range or its Baseline value, study drug may be restarted. If restarting study drug, documentation should include reason that rechallenge is expected to be safe. If after clinically appropriate evaluation, no alternative etiology for ALT or AST elevation is found or the ALT or AST elevation has not resolved or is not trending down toward normal, the subject should be discontinued from study drug.
 
For any confirmed ALT or AST elevations > 3 ULN, complete supplemental hepatic eCRF

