- o. During screening, biologic drug levels may be optionally assessed at the investigator's discretion as an alternative to completing the required washout period: (1) infliximab and natalizumab: may be tested approximately 4 weeks or later from the last dose; (2) adalimumab, certolizumab, golimumab, or vedolizumab: may be tested approximately 6 weeks or later from the last dose; (3) ustekinumab: may be tested approximately 8 weeks or later from the last dose.
- p. The Central Laboratory will perform the urinalysis macro and micro (if applicable). A microscopic analysis will be performed by the central laboratory, in the event the dipstick results show leukocytes, nitrite, ketone, protein, blood or glucose value of greater than a trace. Sites will not be provided with urinalysis dipsticks.
- q. A serum pregnancy test will be performed on all women of childbearing potential at Screening. In Substudy 1 and Substudy 2 Part 1 urine pregnancy test will be performed at the site at Baseline and at Weeks 2, 4, 6, 8 and PD Visits and in Substudy 2 Part 2 it will be done at Weeks 10, 12, 14, and 16, and a home pregnancy test will be performed at the 30-Day Follow-up Visit for all women of child bearing potential. If any urine pregnancy test is positive, a serum pregnancy test will be performed by the central laboratory. If a pregnancy is identified, the pregnancy must be reported to AbbVie as outlined in Section 6.1.6.
- r. Subjects will be tested for the presence of the hepatitis B and C virus (HBV and HCV) at Screening. A positive result for the hepatitis B surface antigen (HBs Ag) or hepatitis C (HCV RNA detectable for any subject with positive anti-HCV AB) will be exclusionary. For subjects who are negative for HBsAg but positive for core antibody (HBcAb), HBV DNA PCR will be performed and any result that meets or exceeds detection sensitivity will be exclusionary. HBV testing is done every 12 weeks where required.
- s. For Japan subjects only: Subjects with positive HBs Ab and/or positive HBc Ab results at Screening in Substudy 1 or 2 should have HBV-DNA PCR test performed at Week 8 in the induction period; in cases where recurrence of HBV-DNA is observed, the subject should be discontinued from the study. This measure is not necessary in patients with history of HBV vaccination and positive HBs Ab result.

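### Protocol Section 5.3.1.1 both requires and waives a screening HBV DNA test for two antibody patterns: unvaccinated anti-HBs-positive, anti-HBc-negative subjects, and vaccinated anti-HBs-positive subjects in Japan

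*Protocol*

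**What the plan says.** Section 5.3.1.1 (Hepatitis Screen) sets out the screening rule as bullets and as Figure 4 with its notes.

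- Bullet on negative anti-HBc: "A negative test result for HBc Ab does not require HBV DNA PCR qualitative testing and the subject may be enrolled (Scenarios A and B").
- Bullet on positive anti-HBc: "A positive test result for HBc Ab requires HBV DNA PCR testing (automatic reflex testing) (Scenarios C and D").
- Bullet on vaccinated subjects: "For a subject who has had an HBV vaccination (should document in the medical history), a positive test result for HBs Ab is expected". It goes on to waive the HBV DNA test and allow enrolment (Scenario B).
- Figure 4, single-asterisk note: "For subjects without a history of HBV vaccination (and for subjects in Japan) a positive result for HBs Ab/anti-HBs requires HBV DNA PCR testing".
- A further bullet makes any positive HBV DNA result exclusionary.

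Two other places bear on screening. Exclusion criterion 27 (Section 5.2.2) excludes on detected HBV DNA in anti-HBc-positive subjects, with an extension in brackets: "and for Hepatitis B surface antibody positive (+) subjects where mandated by local requirements". Appendix C note r states: "For subjects who are negative for HBsAg but positive for core antibody (HBcAb), HBV DNA PCR will be performed". It does not mention anti-HBs as a trigger. Table 1 lists the HBV DNA test as a reflex test only.

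**The concern.** The bullets make anti-HBc status decide whether the HBV DNA test is done. The Figure 4 note makes anti-HBs status decide it, together with vaccination history or being in Japan. The two approaches disagree for identifiable subjects. Because a positive result is exclusionary under Section 5.3.1.1, the choice of rule can change eligibility and not only the list of tests.

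This is a safety-related entry rule for an immunomodulatory drug. Two sites following different sentences of the same section could handle identical subjects differently, and each could point to the protocol in support. There is also a practical gap. The only reflex that the section names is triggered by anti-HBc, whereas the note depends on vaccination history, which is held in the medical history. The text does not say who orders the test that the note requires.

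**Working it through.** No figure is involved, so the check applies each printed rule to two subject profiles. Both are HBsAg negative, anti-HBc negative and anti-HBs positive.

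- Profile 1: no vaccination history, outside Japan, no local mandate.
- Profile 2: documented vaccination, in Japan.

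| Rule | Profile 1 | Profile 2 |
|---|---|---|
| 5.3.1.1, negative anti-HBc bullet | no test; may be enrolled | no test; may be enrolled |
| 5.3.1.1, vaccinated bullet | not addressed | no test; may be enrolled |
| 5.3.1.1, positive anti-HBc bullet (reflex) | not triggered | not triggered |
| Figure 4, single-asterisk note | test required | test required |
| Exclusion criterion 27 | not reached | reached only if Japan counts as a local mandate, which the criterion does not say |
| Appendix C note r | not named | not named |

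**Profile 1.** The bullet and the note conflict outright: the bullet has no vaccination condition, and the note has no anti-HBc condition. Criterion 27 and note r do not say that the subject may be enrolled untested. They confine the test, or the exclusion that rests on it, to anti-HBc-positive subjects, and so omit what the note requires. A local mandate brings criterion 27 into line with the note but leaves the bullet and note r unchanged.

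**Consequence of a positive result in Profile 1.** If the test is run under the note and is positive, Section 5.3.1.1 makes the result exclusionary. Criterion 27 does not reach this subject without a local mandate. The procedures text and the numbered criterion therefore give different answers on eligibility.

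**Profile 2.** The Japan clause adds something only if it reaches vaccinated subjects, because unvaccinated subjects are already covered by the words before it. Read that way, it conflicts with the waiver in the vaccinated bullet. The on-study rules for Japan follow a different line: Appendix C note s (Week 8) and Appendix E note p (Weeks 4 to 52) require HBV DNA testing in Japanese subjects positive for either antibody, but exempt those who are vaccinated and anti-HBs positive. These are different tests at different times, so they do not contradict the note. They do show vaccination status being treated differently at screening and during the study.

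**Who could be affected.** Substudies 1 and 2 plan 382 + 462 = 844 subjects in total. The documents do not say how many have either pattern. Subjects entering Substudy 3 from Study M14-675 were screened under a protocol not supplied here, and Section 5.1.2 does not require them to meet this protocol's criteria.

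**The case against.** The strongest reply is that Figure 4 governs and is not visible in the supplied text. The vaccinated bullet introduces Scenario B with a vaccinated subject, so Scenarios A and B may never have been meant to cover the unvaccinated profile, and the note would then be the specific exception. That reading is possible. It does not settle the matter, because the negative anti-HBc bullet is printed without an exception, and criterion 27 and note r do not repeat the note's requirement.

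A reader might infer three stronger things that the documents do not support.

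- **That several passages expressly enrol the unvaccinated profile untested.** Only the Section 5.3.1.1 bullet does. Criterion 27 and note r are narrower than the note, which is a gap rather than an opposite instruction.
- **That subjects missed at screening go unmonitored for up to 16 + 52 = 68 weeks.** The HBV DNA trigger in Table 5 does cover only "Subjects with HBc Ab+ (irrespective of HBs Ab status) and negative HBV DNA PCR testing at screening". However, drug interruption and a search for another cause at the ALT/AST thresholds in the same table apply whatever the antibody status. The Figure 4 notes also allow unscheduled HBV DNA testing and provide 12-weekly testing where mandated, and the Japan notes add more. Table 5 is a separate on-study rule and contradicts nothing here.
- **That the count of entry-criteria deviations shifts.** Section 7.0 counts subjects who did not satisfy entry criteria. Omitting a test that only the note requires is not, by itself, such a deviation.

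Two more points stand. Exclusion criteria 24 and 42 let an investigator exclude a subject with active viral infection on clinical judgement, and no passage instructs enrolment of a subject with positive HBV DNA. Enrolment is also closed in all three substudies, so corrected wording will screen nobody further.

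**Conclusion.** The contradiction is real and lies in the current text. For the unvaccinated anti-HBs-positive, anti-HBc-negative subject, one sentence of Section 5.3.1.1 waives the HBV DNA test and another requires it, and criterion 27 and Appendix C note r do not carry the requirement. For vaccinated anti-HBs-positive subjects in Japan, the waiver and the Figure 4 note conflict.

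The size is limited. It is an inconsistency in a safety eligibility rule. It alters no endpoint, sample size or error rate. The number of subjects cannot be derived from the documents, and differing practice between sites is a possibility that the text allows rather than something it shows. The conclusion assumes that the unseen figure does not itself qualify the printed bullet. If it does, the bullet, criterion 27 and note r would still need to say so. This review takes no position on which rule is right.

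**What to change.** 1. The sponsor should reconcile Section 5.2.2 (criterion 27), the Section 5.3.1.1 bullets, the Figure 4 note and Appendix C note r to one screening rule for the two antibody patterns. The rule should state whether a positive result excludes. Appendix C note s and Appendix E note p should be checked for consistency with it. Table 5 needs no change to resolve the contradiction.
2. Because enrolment is closed, most of the practical gain lies in a listing. From screening data already held, identify enrolled subjects with either pattern and no screening HBV DNA result, and apply the reconciled rule to any still on study drug. Section 8.1 expects that some subjects may remain on blinded treatment after the database lock.

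The cost is wording in four places, a consistency check of the Japan notes and one data listing. The design, sample size and efficacy analyses are untouched.

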5.3.1.2 Collection and Handling of Optional Samples for Exploratory Research and Validation Studies

Subjects will have the option to provide samples for exploratory research and validation studies. Subjects may still participate in the main study even if they decide not to participate in this optional exploratory research/validation study. The procedures for obtaining and documenting informed consent are discussed in Section 9.3.

Exploratory research can help to improve our understanding of how individuals respond to drugs and our ability to predict which subjects would benefit from receiving specific therapies. In addition, exploratory research may help to improve our understanding of how to diagnose and assess/monitor UC by assessing associations between disease characteristics, outcomes data, and biomarkers of interest.

Validation studies, including those related to the development of potential in vitro diagnostic tests, may be carried out retrospectively in order to assess associations between events of interest (i.e., efficacy and/or safety events) and candidate biomarkers.

AbbVie (or people or companies working with AbbVie) will store the biomarker exploratory research/validation studies samples in a secure storage space with adequate measures to protect confidentiality. The samples will be retained while research on upadacitinib (or drugs of this class) or UC and related conditions continues, but for no longer than 20 years after study completion.

The following samples will be collected according to [Appendix D](#) and [Appendix F](#) from each subject who consents to provide samples for exploratory research/validation studies:

- Blood samples for pharmacogenetic and epigenetic analyses (DNA)
- Blood samples for transcriptomic and/or epigenetic analyses (RNA) [if possible, subjects should be fasted for approximately 8 hours prior to collection]

- Serum and plasma samples for systemic analyses including, but not limited to, proteomics and metabolomics (if possible, subjects should be fasted for approximately 8 hours prior to collection)
- Stool for biomarker analysis
- Rectosigmoid biopsy for exploratory research (frozen) and transcriptomic and/or epigenetic analysis (RNA later).

Samples will be shipped to AbbVie or a designated laboratory for DNA/RNA extraction, if applicable, and/or analyses or long-term storage. Instructions for the preparation and shipment of the samples will be provided in the laboratory manual.

COVID-19 Pandemic-Related Acceptable Protocol Modifications

If subject is unable to attend visit where optional exploratory samples are collected, these should not be collected at a local lab.

5.3.2 Drug Concentration Measurements

5.3.2.1 Collection of Samples for Analysis

Blood samples for pharmacokinetics assay of upadacitinib and possibly other concomitant medications will be collected at the following times:

- Substudy 1: Week 2, Week 4, Week 6, and Week 8/PD
- Substudy 2 Part 1: Week 2, Week 6, and Week 8/PD
- Substudy 3: Week 36 and Week 52/PD

On visits where the blood samples for assay of upadacitinib are being collected as noted, samples should be collected prior to dosing and the subjects should take the study drug dose at the clinic after collecting the PK blood sample, when possible. However, if the subject normally takes the study drug dose at a time that is much earlier or after the time of the scheduled study visit, the subject should follow the regular dosing schedule and the PK sample will be collected at any time during the visit.

The date and accurate time of the PK sample collection and the last two study drug doses will be recorded on the applicable requisition forms and in the eCRF to the nearest minute.

Refer to the study specific laboratory manual for detailed instructions on sample collection, processing, and shipment.

COVID-19 Pandemic-Related Acceptable Protocol Modifications

If subject is unable to attend visit where pharmacokinetic samples are collected, these should not be collected at a local lab.

